Goal

The aim of this study is to evaluate the effect of breastfeeding education given by teach-back method on breastfeeding success.

Hypotheses

H0: Breastfeeding training given by Teach-Back method has no effect on breastfeeding success.

H1: Breastfeeding training given by Teach-Back method has an impact on breastfeeding success.

Methods

Study design

This study, which has a randomized controlled experimental research design, was conducted between 15 January and 15 December 2018. The sample of the study was divided into two groups by randomization. Breastfeeding success levels were compared by providing breastfeeding education and counseling service based on the teach-back method to one group of mothers (intervention group), and standard breastfeeding education and counseling service to another group (control group). Opinions were received from five academicians working in the field of Midwifery, Obstetrics and Gynecology Nursing, who have researches on breastfeeding. Recommendations from the CONSORT group (Consolidated Standards of Reporting Trials) were followed in this study (Schulz et al., 2010).

Sample and setting

Women who live in a city center where is in Turkey's Central Anatolia and have a vaginal birth, literate, primipar, in term and healthy. Those excluded from the inclusion criteria were excluded from the study.

The study was carried out in the City Hospital, where the number of births in the city center was the highest in a year, and in the Family Health Centers where maternal and infant follow-ups were performed. The first stage of the study, which was the stage of meeting women, was done in the maternity unit and postpartum service of the City Hospital, since women who gave vaginal births were

discharged after 24 hours if no problem developed. The second stage of the study was carried out in Family Health Centers where women are affiliated.

Sample size calculation

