The universe of the study was composed of women who had vaginal births in the City Hospital between years 2017-2018. According to the hospital records, in the first 6 months of 2017, the total number of births was determined as 1455, and the number of non-invasive vaginal births was 590. The minimum number of individuals to be included in the sample of the study was calculated using the "G-power 3.1.3" program based on the data of the study titled "The effect of antenatal training based on strengthening breastfeeding self-efficacy perception and breastfeeding success" (Tokat Aluş & Okuş, 2013). Considering the sample size of the research and the mean scores obtained from this study, the LACTH scale scores will increase 0.5 points after the application, with the pre-acceptance of the clinical effect to be 5% of Alpha error and 80% of the power of the study (Effect Size: 0.70) and it was determined that there should be at least 31 people in each group (Tokat Aluş & Okumuş, 2013). A total of 80 women, 40 studies and 40 control groups, were included in the sample. Women who had vaginal births meeting the inclusion criteria were selected by simple random randomization into the intervention and control group.

Randomization

Considering the inclusion and exclusion criteria, women were divided into simple randomization intervention and control groups. In the randomization of the sample, "Research Randomizer" was used. The randomization process was created by a neutral researcher who was not involved in the study. The women were not informed about the groups they were in. Single blind was provided in the study by knowing which group they would be in by the researcher.

Intervention

The study was carried out in two stages. In the first stage, in the first 24 hours at the postpartum period, the researcher interviewed the women who gave birth in the postpartum care units of the hospital and

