determined the women who volunteered to participate in the research and that comply with the inclusion criteria and received their informed consent. Women were divided into randomized intervention or control groups. When the postpartum mother and baby's health condition was stable, "Personal Information Form" was applied to mothers. After the women were informed about the appointments and dates at the Family Health Centers where the second phase of the research will be carried out, the home and mobile numbers of the researcher were given to them in writing. The meeting ended with the mothers about the time and place of the next visits.

In the second stage of the study, three interviews were held with the mothers on the dates determined in the first stage of the study. In these interviews, the mothers in the intervention group were asked by the researchers about the needs of breastfeeding by using the relevant literature (Ekşioğlu, 2016; Hannula, Kaunonen, & Tarkka, 2008; Maleki-Saghooni et al., 2017; RNAO, 2018). Training and counseling based on the Teach-back method was given in the Family Health Centers (FHC) where they are registered. Turkey Ministry of Health's Postpartum Care Management Guidelines (2014) was carried out with mothers enrolled in FHC in the control group, on the basis of three interviews. In these interviews, standard training and counseling services were offered on breastfeeding. While providing standard training and counseling services, "Breastfeeding Training Guide" used in the intervention group was taken as the basis. The method of straight expression, which is mostly used by breastfeeding counseling provider healthcare professionals in Turkey, was used. In standard education, whether the learning is achieved is tested by closed-ended, "yes-no" questions structured as "Did you understand?". After, it is controlled by asking whether there are any questions about the subject. The trainings of both groups were given individually in a separate room at FHCs.

Measurements and data collection

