Based on the literature information (Faridvand, Mirghafourvand, Malakouti, & Mohammad-Alizadeh-Charandabi, 2017; Jeon & Hwang, 2013; Maleki-Saghooni et al., 2017; Tarrant, Younger, Sheridan-Pereira, & Kearney, 2011) an information form was developed by researchers. The form consisted of a total of 28 questions, including the socio-demographic and personal characteristics of women in the intervention and control group (16 questions), questions related to birth, postpartum period and

breastfeeding (12 questions). “LATCH Breastfeeding Diagnosis and Evaluation Scale” and “Postpartum Breastfeeding Self-Efficacy Scale Short Form” were used to evaluate breastfeeding success. The Breastfeeding Training Guide used in the education of mothers was created by scanning the literature on the subject (Aittasalo et al., 2006; Badaczewski et al., 2017; Farris, 2015; Tamura-Lis, 2013; Tokat, Okumuş, & Dennis, 2010) and in line with the recommendations of 5 academics specialized in Obstetrics and Gynecology Nursing. In order to evaluate the performance of the researcher using the Teach-back method, the “Teach-Back Method Observation Tool” recommended by the developers of this method was used.

Data Collection

In the first stage of the study, women were interviewed in postpartum care units, and when the health condition of the mother and baby was stable, the Personal Information Form was applied to the mothers.

In the second stage of the study, 3 interviews were conducted with the mothers in the intervention and control groups during the 2-5th postpartum days, 13-17th days and 30-42nd days. In the first meeting of the second phase, the pre-education Breastfeeding Diagnostic Tool LATCH and Postpartum Breastfeeding Self-Efficacy Scale were applied to the mothers in the intervention and control groups. Breastfeeding training and counseling services were provided to the mothers in the intervention group, based on the teach-back method, and those in the control group using the standard breastfeeding training technique. This interview lasted an average of 1 hour.

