In the second meeting of the second stage, which was held between the 13th and 17th days of birth, the pre-education Breastfeeding Diagnostic Tool LATCH and Postpartum Breastfeeding Self-Efficacy Scale were applied to the mothers in the intervention and control groups. Breastfeeding training and counseling services were provided to the mothers in the intervention group, based on the teach-back method, and those in the control group using the standard breastfeeding training technique. This interview took an average of 40-45 minutes.

In the third meeting of the second stage, which was held between the 30-42th days of birth, the pre-education Breastfeeding Diagnostic Tool LATCH and Postpartum Breastfeeding Self-Efficacy Scale

were applied to the mothers in the intervention and control groups. Breastfeeding training and counseling services were provided to the mothers in the intervention group, based on the teach-back method, and those in the control group using the standard breastfeeding training technique. This interview took an average of 40-45 minutes.

Statistical analysis

The data of the study were evaluated on computer by using Statistical Package for Social Sciences (SPSS) (22.0) program. In the evaluation of the data;

- The distribution of the data was evaluated with the Kolmogorov-Smirnov test. Since it showed a normal distribution, parametric tests were used in the analyzes.
- The homogeneity of the groups was assessed by chi-square test in categorical variables, Mann Whitney U in numerical variables, or T test in independent groups.
- In the intervention and control groups, “Multifaceted Variance Analysis in Repeated Measurements” was performed in comparing the LATCH breastfeeding diagnosis and evaluation scale and the breastfeeding self-efficacy scale according to the group, time and group * time interaction.
- In the advanced analysis of the difference between the LATCH, breastfeeding diagnostic and evaluation scale, and breastfeeding self-efficacy scale averages in the intervention and control groups, “One-Way Variance Analysis in Repetitive Measurements” to compare the mean scores of the groups within themselves, “Bonferroni Correction Dependent Groups T-Test” to compare the measurements with each other.

Ethical consideration

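### Does it call for a change that the last LATCH and self-efficacy scores are taken before the third education session?

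*SAP*

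**What the plan says.** The Goal section states the aim as "to evaluate the effect of breastfeeding education given by teach-back method on breastfeeding success". The hypotheses use similarly general terms, and neither mentions how many sessions make up the education. The Intervention section sets out the contacts: "In the second stage of the study, three interviews were held with the mothers on the dates determined in the first stage of the study".

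The Data Collection section places these interviews at days 2-5, 13-17 and 30-42 after birth. It gives the order of events within each:

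- First meeting: "In the first meeting of the second phase, the pre-education Breastfeeding Diagnostic Tool LATCH and Postpartum Breastfeeding Self-Efficacy Scale were applied", and then the education.
- Second meeting: "In the second meeting of the second stage, which was held between the 13th and 17th days of birth, the pre-education Breastfeeding Diagnostic Tool LATCH", with the self-efficacy scale alongside it, and then the education.
- Third meeting: "held between the 30-42th days of birth, the pre-education Breastfeeding Diagnostic Tool LATCH and Postpartum Breastfeeding Self-Efficacy Scale", and then the education.

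No later visit and no scoring after the third session is described. The Statistical analysis section compares both scales "according to the group, time and group * time interaction", followed by within-group comparisons over time. The Sample size calculation section assumes that "the LACTH scale scores will increase 0.5 points after the application".

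**The concern.** Education is given at three meetings, but the last score is taken before the last teaching. A reader could take the days 30-42 contrast as the effect of the whole programme, when on the written schedule it is the effect of the first two sessions some weeks after the second. The third session, of 40 to 45 minutes in each arm, then contributes to no measured outcome.

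Two further features add to the doubt. The three paragraphs are worded almost alike, so the description of the third scoring might have been carried over from the first meeting by mistake. The sample size also rests on a gain after the education has been applied, and no score follows all of it. At stake would be the meaning of the final time point and the scope of the conclusion. A difference in treatment between the arms is not at issue.

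**Working it through.** **Inputs.** Meeting windows of days 2-5, 13-17 and 30-42, scoring before teaching at each meeting, and one session per meeting (Data Collection). No education is described in the hospital stage (Intervention, Data Collection). Scoring and teaching are taken to fall on the same day within a meeting.

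**Sessions completed before each score**

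| Score | Window | Prior sessions | Days since previous session |
|---|---|---|---|
| 1 | days 2-5 | 0 | none (baseline) |
| 2 | days 13-17 | 1 | 13 - 5 = 8 to 17 - 2 = 15 |
| 3 | days 30-42 | 2 | 30 - 17 = 13 to 42 - 13 = 29 |

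The count is 0, 1 and 2 of 3 in both arms. The factual part of the concern is correct.

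**Effect on the test.** If teach-back made no difference compared with standard education, the two randomised arms would have the same expected scores at every time point, wherever the scoring falls relative to the teaching. The schedule is common to both arms, so the group-by-time test keeps its meaning under the null hypothesis. Under the alternative, scores 2 and 3 both follow teach-back education in one arm and standard education in the other. A difference there is evidence for the stated hypothesis, which requires no particular number of sessions.

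**If the third description were a slip.** The last score would then follow 3 sessions, 0 days after the last. The model, its terms and the test would be the same. Only the verbal description of the last time point would differ.

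**Effect on the sample size.** The plan states at least 31 per group for an effect size of 0.70, alpha of 5% and power of 80%. It does not state the sidedness. The two-sided normal formula gives

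n = 2(1.960 + 0.842)² / 0.70² = 2 × 7.85 / 0.49 = 32.04, rounded up to 33 per group.

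The two-sided t calculation gives 34, and a one-sided calculation gives 26. The planned 40 per group exceed all of these, with two-sided power of about 87% at 0.70. The timing of the scores enters none of these figures.

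**Could a loss of power be put on it?** Only by assumption. If the effect after two sessions were 80% of 0.70 (0.56), power with 40 per group would be about 70%. At two thirds (0.47) it would be about 54%. The plan gives no effect per session and does not tie 0.70 to three sessions, so these fractions have no support in the document and cannot be used to size the issue.

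**The case for a change.** The strongest case for a change is that the SAP sets out both the schedule and the analysis, yet never says what exposure each time point represents. The Intervention section describes three interviews, the sample size speaks of a gain after application, and the final contrast invites a three-session reading. A check of the records and two or three sentences would remove the doubt at almost no cost.

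What stands is the count of sessions, and that a report would be clearer for stating it. The rest does not carry.

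- The order is already given in each of the three meeting paragraphs, without contradiction. Any reader of that section can work out the exposure behind each score.
- Nowhere does the SAP claim a three-session effect, so there is no overstatement to correct.
- Similar wording for similar visits does not show a copying error. The stated duration differs between the first meeting (about 1 hour) and the later two (40 to 45 minutes), so the text was not repeated unchanged.
- The sample-size phrase does not say that all sessions must be complete. Scores 2 and 3 both come after education has been given.
- Rewording the goal of a study already conducted in 2018 so that it fits the measurement schedule would be poor practice.

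Scoring before teaching is also a reasonable trade-off. It applies one rule at all visits and preserves a real baseline. It measures what the mother retains a week or more after teaching, where a score on the day of the third session would mix same-day performance with delayed scores. The price is that the third session is not evaluated.

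**Conclusion.** No change to the plan is needed. As written, the days 30-42 score follows two of the three sessions by 13 to 29 days, and no outcome is measured after the third. This is a consistent and openly stated design feature, equal in both arms. It introduces no bias between them, leaves the test of the null hypothesis valid, and alters no test, estimate or sample-size figure. A sentence in the report's limitations saying that the last score precedes the third session would be helpful but is optional.

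This rests on taking the order in Data Collection as written and on scoring and teaching falling on the same day within each meeting. If the third score was in fact taken after the teaching, the conclusion about the plan would be the same, and only the description of that time point would differ.

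### Comparability of the arms is judged by significance tests and the outcome comparison is adjusted for no form item; adjustment fixed in advance would gain precision and correct for chance imbalance in the chosen variables

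*SAP*

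**What the plan says.** The Statistical analysis section of the SAP states "The homogeneity of the groups was assessed by chi-square test in categorical variables" and names the Mann-Whitney test or the independent-samples t-test for numerical variables. It gives no significance level for these tests, no list of variables and no consequence of a result.

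The outcome model for LATCH and self-efficacy contains arm, time and their interaction. The further analyses (one-way repeated-measures ANOVA within groups, Bonferroni-corrected paired t-tests) look at change within groups. No covariate appears in any of them.

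Baseline data are available. Under Measurements and data collection, "The form consisted of a total of 28 questions": 16 socio-demographic and personal, 12 on birth, the postpartum period and breastfeeding. Under Data Collection, both scales are also taken at the first second-stage meeting (days 2 to 5), before any training. Randomization describes simple allocation, and no stratification is stated.

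**The concern.** A non-significant test with 40 women per arm does not show that the arms are alike; it shows only that the difference fell below a threshold set by the sample size. Nor does a significant result show that the comparison is distorted. Women were randomised, so any imbalance is due to chance. Its effect on the result is the size of the imbalance multiplied by the strength of the variable's link with the outcome, and the p-value measures only the first of these.

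Under the plan as written, a moderate chance imbalance in a prognostic item can be labelled homogeneous and left in the between-arm comparison. The precision that already collected prognostic variables could give goes unused.

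**Working it through.** **Inputs from the SAP.** 40 per arm, 5% alpha, 80% power, "Effect Size: 0.70" (Sample size calculation). The 5% is stated for the sample size only; I assume it for the homogeneity tests too. Sidedness is not stated; two-sided is assumed because the hypothesis has no direction: "H1: Breastfeeding training given by Teach-Back method has an impact on breastfeeding success". The correlation r between a baseline variable and the outcome is not given; 0.3 to 0.5 is an assumed range.

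**The plan's own figure.** The SAP says "it was determined that there should be at least 31 people in each group". The normal approximation gives 2 × (1.960 + 0.842)² / 0.70² = 32.04, so 33; the exact two-sided t-test gives 34. The stated 31 is close but not exact. The 40 enrolled per arm exceed all three, so nothing below depends on this.

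**What the tests let through.**
- Numerical: t(0.975, 78 df) × √(2/40) = 1.991 × 0.2236 = 0.445 SD. That is 0.445 / 0.70 = 64% of the design effect.
- Categorical: 16/40 versus 24/40 gives chi-square = 4 × (4²/20) = 3.20, p = 0.074, which passes. 15/40 versus 24/40 gives 4.05, p = 0.044, which does not. With a continuity correction the latter also passes (p = 0.074).

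**How often.** By construction, a given item exceeds 0.445 SD by chance about 5% of the time. The median absolute imbalance is 0.6745 × 0.2236 = 0.15 SD.

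**Shift in an unadjusted comparison of follow-up scores** (r × imbalance):

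| Imbalance | r = 0.3 | r = 0.5 |
|---|---|---|
| 0.445 SD | 0.13 SD (19% of 0.70) | 0.22 SD (32%) |
| 0.15 SD | 0.045 SD (6%) | 0.075 SD (11%) |

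Given an imbalance of 0.445 SD, the follow-up difference under no effect has mean 0.445r and variance 2(1 − r²)/40. It is tested against 1.96 × √(2/40). The two-sided error rate conditional on that imbalance is about 8% at r = 0.3 and 13% at r = 0.5.

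**Shift in arm-by-time.** For a form item, the change from the first meeting to a later one shifts by (r at follow-up − r at first meeting) × 0.445. This is zero if the two correlations are equal. With 0.5 and 0.3 it is 0.2 × 0.445 = 0.09 SD, or 13% of 0.70, the most that the assumed range allows.

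**Imbalance in the first pre-education score itself.** The interaction treats this score as the start of a change. The change contrast then shifts by (r − 1) × 0.445: −0.31 SD at r = 0.3 and −0.22 SD at r = 0.5. Here the change over-corrects, and analysis of covariance (ANCOVA) does not.

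**Precision.** The variance factor is 1 − r² for ANCOVA and 2(1 − r) for the change, a ratio of (1 + r)/2. ANCOVA is therefore never less precise, apart from the degree of freedom used. Power at 40 per arm for 0.70 (normal approximation, one follow-up occasion):

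| Analysis | r = 0.3 | r = 0.5 |
|---|---|---|
| Follow-up score, unadjusted | 87.9% | 87.9% |
| Change from first meeting | 75.4% | 87.9% |
| Follow-up score, ANCOVA | 90.7% | 95.1% |

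**The case against.** The strongest reply is that the planned analysis is valid. Under randomisation the unadjusted test keeps its 5% level over all allocations, and unadjusted power at 40 per arm is already 87.9% for the design effect. That stands. A reader might infer from the conditional error rates of 8% and 13% that the trial's type I error is inflated; it is not. Those rates apply only given an imbalance at the edge of the 5% tail, and the typical shift is a third of that size.

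A second reply is that the repeated-measures model already uses the baseline scores. It does, as the first occasion, and this removes much or all of a form item's effect from the interaction. A reader might carry the 19% to 32% over to arm-by-time; that is not supported. Those figures belong to a comparison of follow-up scores. An item that predicts all occasions equally carries the same shift into the group main effect, which the plan also tests. The treatment of the baseline score as a change remains less precise than ANCOVA.

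A reader might also infer that the tests decide which covariates are adjusted for, or that false alarms across 28 items alter the analysis. The SAP says neither: it attaches no consequence to a test and does not say which items are tested. Likewise, the power of these tests to detect a true imbalance is not a meaningful quantity here, because under randomisation there is no population difference to detect.

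Two practical cautions hold. The study ran from January to December 2018 and the SAP already reports the distribution of the data, so naming covariates in advance may no longer be possible. The Intervention section also places the form after allocation, and Randomization says that the researcher knew the groups, so items open to influence by that knowledge are poor choices.

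**Conclusion.** The point holds as a cheap improvement, not as a flaw that invalidates the trial. The homogeneity tests pass imbalances up to 0.445 SD or 40% versus 60%, given two-sided 5%, and no form item is adjusted for. The likely cost is small: 0.05 to 0.08 SD at a median imbalance in a single item, 0.13 to 0.22 SD at the 5% tail, in a comparison of follow-up scores, and less in arm-by-time. These sizes rest on the assumed r of 0.3 to 0.5; the documents give no figure from which to narrow it. Adjustment corrects only for the variables included. Deleting the p-values alone would change no result; the gain comes from the adjusted comparison.

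**What to change.** 1. Replace the homogeneity tests with a descriptive table by arm, without p-values.
2. Make the between-arm comparison of follow-up LATCH and self-efficacy scores (days 13 to 17 and 30 to 42) an adjusted analysis. Adjust, whatever the observed balance, for the first-meeting score of the same scale and a few form items that allocation cannot influence, for example maternal age and schooling if they are on the form. Specify the first-meeting score by name, because the SAP calls the scores at all three meetings pre-education.
3. If the repeated-measures model is kept, add covariate-by-time terms. With complete data, a covariate entered only as a main effect leaves arm-by-time unchanged.
4. Report the unadjusted result as a sensitivity analysis.
5. If the data have already been seen, choose the covariates on literature grounds and disclose the choice as post hoc.

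The cost is revised SAP wording and a few degrees of freedom out of 80 women. No new data are needed. The gain depends on how strongly the chosen variables predict the outcome.

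### The between-arm analysis is a repeated-measures ANOVA with no missed-visit rule and no sphericity correction; a mixed model in the same software would guard against both at little cost.

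*SAP*

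**What the plan says.** The Statistical analysis section states that the data were analysed with the "Statistical Package for Social Sciences (SPSS) (22.0) program". Both scales (LATCH and breastfeeding self-efficacy) are compared by "Multifaceted Variance Analysis in Repeated Measurements", "according to the group, time and group * time interaction". The follow-up tests are "One-Way Variance Analysis in Repetitive Measurements" within each arm and "Bonferroni Correction Dependent Groups T-Test" between pairs of measurements.

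The scores come from three interviews at Family Health Centers, "during the 2-5th postpartum days, 13-17th days and 30-42nd days" (Data Collection). The first score is taken before any education. Randomisation comes earlier, in hospital (Intervention). The Sample size calculation section requires at least 31 women per arm for an effect size of 0.70, then states: "A total of 80 women, 40 studies and 40 control groups, were included in the sample". It does not call the surplus a dropout allowance.

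The SAP does not name the SPSS procedure, the analysis population, a rule for missed visits, a sphericity test, or which within-subject test is read.

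**The concern.** Two properties of the named method matter.

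**Incomplete women.** Classical repeated-measures ANOVA needs every score from every woman. Attendance was spread over about six weeks at outpatient centres, so missed visits are a credible risk. A woman who missed one visit would lose her remaining scores as well. If missing a visit relates to how breastfeeding is going, and differently by arm, the comparison of those who remain may be biased.

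**Sphericity.** The uncorrected within-subject F-tests are exact only if all visit-to-visit differences have equal variance. If that fails, the group-by-time test rejects too often. This is the test that carries most of the treatment question, because the first score precedes any education and the group main effect averages it in. None of the listed follow-up tests gives a between-arm difference at a visit with a confidence interval.

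**Working it through.** **1. The plan's sample size.** Inputs: effect size 0.70, alpha 5% (taken as two-sided), power 80%. n per arm = 2(1.960 + 0.842)²/0.70² = 32.04, rounded up to 33. The t-based calculation gives 33.02, rounded up to 34. Both are close to the stated 31. Falling from 40 to 31 per arm is a loss of 1 − 31/40 = 22.5%, used below as an assumed missing rate.

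**2. Precision lost by complete cases.** Target: the visit-3 arm difference adjusted for the first score, in SD units. This measures the cost of discarding incomplete women; it is not the plan's own F-test. Assumptions: 9 of 40 per arm miss visit 2 or visit 3, and the visit correlations are as shown.

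- Complete cases: variance = (2/31)(1 − r₁₃²). With r = 0.5 this is (2/31)(0.75) = 0.0484.
- All available scores: add the information from the 31 complete women, 4.5 with visit 2 only and 4.5 with visit 3 only. With r = 0.5, the covariance of visits 2 and 3 given baseline has diagonal 0.75 and off-diagonal 0.25. The information matrix has diagonal 46.5 + 4.5/0.75 = 52.5 and off-diagonal −15.5. Variance = 2 × 52.5/(52.5² − 15.5²) = 0.0417.
- Standard error ratio = √(0.0484/0.0417) = 1.08.

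| Correlations (1-2, 2-3, 1-3) | Complete cases | All scores, even split | SE ratio, even split | SE ratio, all 9 miss visit 3 |
|---|---|---|---|---|
| 0.5, 0.5, 0.5 | 0.0484 | 0.0417 | 1.08 | 1.01 |
| 0.7, 0.7, 0.7 | 0.0329 | 0.0282 | 1.08 | 1.02 |
| 0.5, 0.8, 0.4 | 0.0542 | 0.0443 | 1.11 | 1.07 |

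So the standard error is 1-11% larger, depending on pattern and correlation. At 5% missing, evenly split, it is 1.4-2.0% larger.

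**3. Power at the planned 0.70.** Power = Φ(0.70/√variance − 1.96). Even split: 89% (complete cases) against 93% (all scores) in the first row, and 85% against 91% in the third. The second row is higher on both sides. An unadjusted two-sample t-test has less room: 87.1% with 40 per arm and 77.4% with 31.

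**4. Sphericity.** Visit-window midpoints are about days 3.5, 15 and 36, so the gaps are about 11.5 and 21 days. The group-by-time test was simulated with no arm effect, 40 per arm, 20,000 trials per setting. Epsilon is the Greenhouse-Geisser index (1 = sphericity).

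| Assumed covariance | Epsilon | Uncorrected | Greenhouse-Geisser |
|---|---|---|---|
| Equal correlation 0.5 | 1.00 | 5.0% | 4.9% |
| Decay with days, 0.4 at 11.5 days | 0.94 | 5.0% | 4.6% |
| Decay, 0.6 | 0.89 | 5.4% | 4.8% |
| Decay, 0.8 | 0.82 | 5.8% | 4.9% |
| Decay, 0.9 | 0.79 | 6.3% | 5.2% |
| Equal correlation 0.5, SD 1.6, 1.2, 0.7 | 0.88 | 5.4% | 4.8% |
| Decay 0.6, same SDs | 0.86 | 5.9% | 5.1% |
| Near the three-visit extreme | 0.50 | 8.4% | 5.2% |

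A separate set of 6,000 trials per setting, with other unequal correlations, gave 5.6-6.8% uncorrected and 4.3-4.9% corrected. The group main effect stayed at 4.8-5.3% in the tabulated settings.

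**5. What the main effect estimates.** If the effect is δ at visits 2 and 3 and zero at the first score, the main effect estimates (0 + δ + δ)/3 = 0.67δ, which is 0.47 for δ = 0.70.

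**6. Complete data.** With nobody missing and 0.5 SD at both follow-ups, simulated power of the baseline-adjusted visit-3 contrast against the interaction F-test was 71% v 62%, 88% v 86% and 66% v 58% (the last with Greenhouse-Geisser) for the three correlation sets in step 2. The 0.5 SD is illustrative; the plan's effect is 0.70.

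**The case against.** A reader might infer that this analysis did drop women, did bias the arm difference and did inflate the interaction test. The document supports none of these as fact.

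- **No missed visit is reported.** The SAP is in the past tense and describes three interviews as held and both scales as applied each time. With complete data nobody is dropped. The 22.5% is an assumption taken from the sample-size surplus. Any figure for bias would need an assumed missingness mechanism that differs by arm, and the document offers none.
- **The planned power is not shown to fail.** At 0.70 the baseline-adjusted contrast keeps more than 80% power under the assumed loss.
- **An uncorrected test is not stated.** SPSS repeated-measures output also gives Greenhouse-Geisser, Huynh-Feldt and multivariate results, and the SAP does not say which was read.
- **Unequal spacing does not itself break sphericity.** With equal correlations and variances the error is 5.0% at any spacing. The Bonferroni paired t-tests do not need sphericity either.
- **A mixed model does not restore every randomised woman.** The first score comes after randomisation, so women without it, or without any follow-up score, still contribute nothing to a baseline-adjusted model.

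All of this stands, and it makes the harms conditional and modest. What remains is that the named method needs complete scores in its classical form, and that the missed-visit rule and the choice of within-subject test are left open.

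**Conclusion.** The point holds as an improvement worth making, not as a demonstrated error in the result. Under an assumed 22.5% loss per arm, complete-case analysis makes the visit-3 standard error about 1-11% larger. Bias arises only if missingness relates to outcome, and its size cannot be derived from the document. If correlations fall with time or variances differ, an uncorrected group-by-time test runs at about 5-6.8%; it reaches 8.4% only near the extreme for three visits. The main effect keeps its size but is diluted by a score that the intervention cannot have changed. The correlations, variances and missing rates are all assumptions.

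**What to change.** Replace the ANOVA as the between-arm analysis with a linear mixed model (SPSS MIXED, REML, unstructured covariance). The outcomes are the visit-2 and visit-3 scores. The fixed effects are arm, visit, arm-by-visit, baseline score and baseline-by-visit. Analyse women as randomised, using all available scores. Report the arm difference at visit 3 with its 95% CI. State by arm how many randomised women have no baseline score or no follow-up score.

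If the ANOVA is kept, report Greenhouse-Geisser-corrected or multivariate p-values, and state how women with a missed visit are handled.

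The cost is revised SAP wording and slightly more analysis work in the same software, with no new data. The mixed model relies on scores being missing at random. The study ran from January to December 2018 and the SAP already describes the data's distribution, so the change must be labelled as made after data collection and shown beside the ANOVA.
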